## 2. Objectives and Endpoints

### 2.1. Main Objectives:

- To establish a baseline profile for individual study subjects and monitor them longitudinally to identify deviations that develop over time and may be relevant to human health and healthy longevity.
- To identify the modality that has the highest impact on the identification of deviations from baseline profile.

### 2.2. Main Endpoints:

- The number of new deviations from a study subject's baseline profile 12 months after enrollment that were previously not known at time of enrollment
- The number of new deviations not known at the time of enrollment, at the following timepoints after enrollment:
  - 6 months after enrollment
  - 18 months after enrollment
  - 24 months after enrollment
- The number of new deviations identified by each employed modality

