Objectives	

• The primary objective is to establish a baseline profile for individual healthy study subjects using various modalities and monitor them longitudinally to identify deviations that develop over time and may be relevant to human health and longevity. The secondary objective is to identify the modality that has the highest impact on the identification of deviations from baseline profile.

Adverse Event (AE) Monitoring	Adverse events associated with the study procedures, of venipuncture, non-invasive imaging and functional tests will be reported, although they are expected to be limited due to the nature of these common procedures.

Inclusion Criteria	To participate in the study, patients must meet the following criteria;						
	
 
1. Male or non-pregnant female; age 18 to 90.
 
2. Absence or presence of any medical history or any signs or symptoms of any disease.
 
3. Women of childbearing potential (WOCBP) must have a negative urine pregnancy test (UPT) at all visits.
 
						
Exclusion Criteria	Patients who meet any of the following criteria will be excluded from study participation;						
	
 
1. Unwillingness or inability to participate in the study
 
2. Unwillingness or inability to provide written Informed Consent Form
 
3. WOCBP with positive pregnancy test at enrollment or at any visit
 
						
Study Schedule	Event	Baseline Visit	6-Month Visit $\pm$ 1month	12-Month Visit $\pm$ 1month	18-Month Visit $\pm$ 1month	24-Month Visit $\pm$ 1month	36-Month Visit $\pm$ 1month
	Informed Consent	X					
	Review of Inclusion/Exclusion Criteria	X					
	Medical history and physical exam	X	X	X	X	X	X
	UPT for WOCBP	X	X	X	X	X	X
	Whole Genome Sequencing Analysis	X					
	Biochemical/Omics Analysis	X	X	X	X	X	X
	Non-Invasive Imaging	X	X	X	X	X	X
	Functional Assessments (as needed)		X	X	X	X	X
	Wearables and Quantified Self Assessments (as needed)		X	X	X	X	X
	Adverse Event Monitoring	X	X	X	X	X	X

1. UPTs must have a minimum sensitivity of 25 mIU  $\beta$ -hCG/mL.

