#### 3.1. Study Schema

**Figure 1. Overall Study Schema.** The Baseline Visit includes a Medical history and physical examination (PE) Genomic Analysis, Biochemical/”Omics” Analysis and Non-Invasive Imaging. Subsequent visits at 6 months, 12 months, 18 months, 24 months and 36 months include slightly modified and targeted Medical history and PE, Biochemical/”Omics” Analysis and Non-Invasive Imaging, based on prior findings. Functional Assessments and Wearables and Quantified Self Assessments are included at the 6 months, 12 months, 18 months, 24 months and 36 months visits as determined by the Medical history and PE at the baseline visit.

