## 6. Data Management

Following completion of the consenting process (including informed consent and Authorization for Use/Disclosure of protected health information (PHI)) and it has been determined that the patient meets all of the inclusion and none of the exclusion criteria, enrollment will occur, and data collection will commence.

A secure Electronic Data Capture (EDC) and data management system will be used for entry, storage, review, and management of study data. The system will be compliant with applicable GCP and regulatory requirements. Investigators are responsible for accurate completion and timely submission of the data collected during the study. Sites will be trained in the use of the EDC system for entering study data and uploading supporting documents and will be given access for this purpose.

Quality assurance procedures will be established to ensure that complete, accurate and timely data are submitted, protocol requirements are followed, and that AEs are correctly reported. The management and retention of these data will be compliant with applicable regulatory requirements.

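### Functional and wearable tests have no scheduled baseline, so long-standing findings can enter the 6/18/24-month and per-modality counts of new deviations

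*Protocol*

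**What the plan says.** The first main objective (section 2.1) is to establish a profile for each participant and to "monitor them longitudinally to identify deviations that develop over time". The second is to find the modality that contributes most to identifying deviations from that profile.

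Section 2.2 sets three count endpoints:

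- **12 months:** "The number of new deviations from a study subject's baseline profile 12 months after enrollment that were previously not known at time of enrollment".
- **6, 18 and 24 months:** "The number of new deviations not known at the time of enrollment, at the following timepoints after enrollment".
- **By modality:** "The number of new deviations identified by each employed modality".

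Only the 12-month bullet refers to the baseline profile.

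In the synopsis schedule, the row that begins "Functional Assessments (as needed" has a blank Baseline Visit cell and marks at the five later visits. The wearables row is the same. Section 3.1 agrees: its list of Baseline Visit content omits both groups, and it states that "Functional Assessments and Wearables and Quantified Self Assessments are included at the 6 months, 12 months, 18 months, 24 months and 36 months visits", with participants chosen for them "as determined by the Medical history and PE at the baseline visit".

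**The concern.** A count of deviations that arise during follow-up needs an earlier value to compare with. Section 1.2 makes the same argument when it proposes using each person as their own control. For functional and wearable tests, the first follow-up measurement is the first measurement of any kind under the schedule. An eye or EEG abnormality of many years' standing, unknown to the participant and first seen at 6 months, fits the wording of the 6-month and per-modality bullets. Yet it did not develop during the study.

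Eligibility (section 3.2.1) admits people with any medical history, signs or symptoms, so such findings are to be expected. Because the baseline history and examination decide who gets these tests, the reason for testing can itself predate the first measurement.

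At stake is mainly the modality comparison. History and examination, omics and imaging can be set against their own baseline. Functional and wearable tests at first use cannot. Counting the two kinds together favors modalities that were not used at baseline. The analysis is descriptive (section 7), so these counts are themselves the result.

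**Working it through.** The protocol states no rate, sample-size derivation or expected count, so there is no figure to reproduce. The check sets the endpoint wording against the schedule and then illustrates the possible size.

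**1. Schedule against endpoint** (synopsis schedule; sections 3.1 and 3.3.2)

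| Modality scheduled at follow-up | Scheduled at baseline |
|---|---|
| History and physical examination | Yes |
| Biochemical/omics | Yes |
| Non-invasive imaging | Yes |
| Functional assessments | No |
| Wearables/quantified self | No |

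So 2 of 5 follow-up modalities lack a scheduled baseline. The tests listed under them in section 3.3.2 are 6 functional (VO2-max, endothelial function, EEG, EMG, ophthalmologic examination, optional sleep study) plus 3 wearable (ambulatory ECG, continuous glucose monitoring, ring or similar). That makes 6 + 3 = 9. These figures count list entries, not participants or findings.

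**2. Illustration: assumed undetected duration**

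Assume findings arise at a constant rate r and stay present but undetected for an exponentially distributed time with mean D, in steady state. At a first test at time w after baseline:

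- findings present: r × D
- of these, begun before baseline: r × D × exp(−w/D)
- share begun before baseline: exp(−w/D)
- first-test count divided by truly new count: 1/(1 − exp(−w/D))

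| D (assumed) | Share, first test at 6 months (w = 0.5 y) | Ratio at 6 months | Share, first test at 12 months (w = 1 y) |
|---|---|---|---|
| 0.5 y | exp(−1) = 0.368 | 1/(1 − 0.368) = 1.58 | exp(−2) = 0.135 |
| 1 y | exp(−0.5) = 0.607 | 2.54 | exp(−1) = 0.368 |
| 5 y | exp(−0.1) = 0.905 | 10.51 | exp(−0.2) = 0.819 |

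The share passes one half when D exceeds w/ln 2, which is 0.72 years for a 6-month first test and 1.44 years for a 12-month one.

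**3. Illustration: assumed prevalence and incidence**

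Let p be the prevalence of undetected long-standing findings and i the true 6-month incidence. The long-standing share among findings at first test is p/(p + (1 − p) × i). Sample size and the fraction tested cancel.

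- p = 1%, i = 1%: 0.01/(0.01 + 0.99 × 0.01) = 0.503
- p = 10%, i = 0.1%: 0.10/(0.10 + 0.90 × 0.001) = 0.991

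D, p and i are all assumptions; none is in the protocol. Both illustrations cover only first-use findings without a comparator, not the whole endpoint. An onset-and-duration model also fits continuous measures such as VO2-max, glucose or heart rate variability poorly.

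**The case against.** The strongest reply is that *new* already carries the baseline condition. The protocol ties deviations to the participant's own baseline in several places, including the modality objective in section 2.1, so the shorter bullets may be shorthand. On that reading, a first-use result is not yet a deviation. This is plausible. But it would leave first-use functional and wearable results with no stated place at all, and section 2.2 does not say which reading applies.

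Other replies have partial force:

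- **Known conditions drop out.** A condition recorded in the baseline history was known and is excluded. Only findings not recorded there remain exposed.
- **First recognition is a stated interest.** The study name and section 1.2 point to previously unrecognized findings. These are worth reporting, but they are a different quantity from deviations that arise later.
- **Adjudication, source review or an analysis plan could settle it.** Sections 5.3 and 6.1 help where a baseline record exists, and an analysis plan could restrict the count. None can supply a value that was never scheduled.
- **Section 3.3.2 opens by describing optional functional and wearable assessments at each visit.** The schedule and section 3.1 do not place them at baseline.

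A reader might also infer more than the text supports:

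- **Section 6.** It says that "enrollment will occur, and data collection will commence", which could suggest that even Baseline Visit findings were unknown at enrollment. That is data-management text. Section 2.2 counts months from enrollment and the schedule counts the same months from the Baseline Visit, so the two act as one time origin.
- **Imaging.** The 12-month MR angiogram and the triggered organ MRI might look like the same fault. Baseline CT of head, chest, abdomen and pelvis, CT angiogram of head and neck, X-ray and ultrasound largely supply comparators.

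**Conclusion.** The point holds in a limited form. As written, the 6/18/24-month and per-modality bullets allow pre-existing findings from first-use functional and wearable tests to count as new, and the per-modality comparison then sets unlike counts side by side. The 12-month bullet is less affected because it names the baseline profile.

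The structural extent is 2 of 5 follow-up modalities and all 9 tests listed under them. The effect on endpoint totals or on the modality ranking cannot be derived: the protocol gives no finding rates, and these tests are done only as needed. A reader might conclude from the illustrations that most reported deviations would be pre-existing. The documents do not support that, since the shares depend entirely on assumed inputs and apply only to first-use findings.

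The change should be made, because one of the two main objectives rests on the modality comparison and the remedy is cheap. Confidence is medium, since the shorter bullets may have been meant to carry the baseline condition.

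**What to change.** In section 2.2:

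1. Add to the 6/18/24-month and per-modality bullets the qualifier that ties the deviation to the subject's baseline profile.
2. Count a follow-up finding as new only if comparison with any of that participant's baseline data, from whatever modality, shows it to be new or changed.
3. Report first-use findings without a comparator separately as *first detected, onset unknown*, by modality and next to the new-deviation count.
4. Use that first measurement as the comparator for later visits.

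On the CRF, record for each first-time assessment whether a baseline comparator exists.

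The cost is wording in section 2.2, one CRF field and one more table, with no extra tests, scans or visits. The main count becomes smaller, and some truly new findings without a comparator fall into the separate count. Where no other baseline data serve as comparator, functional and wearable modalities enter the new count only from their second use, so a test done once adds nothing to it. Ranking on that count alone would tilt against them, so the modality comparison should show both counts.

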### 2.3. Exploratory Objectives:

- To assess the impact of introducing leading-edge scientific methods on the number of medications and/or dietary supplements taken by individuals
- To assess the impact of leading-edge scientific methods on the number of *unscheduled* health care visits

### 2.4. Exploratory Endpoints

[figure not shown]
- The number and change in the number of medications taken by an individual at 6 months, 12 months, 18 months, and 24 months after enrollment
- The number and change in the number of dietary supplements taken by an individual at 6 months, 12 months, 18 months, and 24 months after enrollment

- Number of unscheduled, urgent care/emergency department visits within 24 months and 36 months after enrollment
- Number of unscheduled hospital admissions within 24 months and 36 months after enrollment

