### 3. Study Design

This is a prospective, population-based observational study. Participants may be recruited from clinical sites that are actively participating in the Puer Research comprehensive evaluation model. Participants and all participating health care providers are unblinded.

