## 7. Statistical Considerations

By design, the study will not employ formal hypothesis testing. Study endpoints will be described using descriptive statistics, using means and standard deviations, medians with inter-quartile ranges, and other descriptive statistical methods, as appropriate.

Data from participants who discontinue the study prior to completion will only be considered through the date of withdrawal and will not be followed in the remaining longitudinal study endpoints.

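### The change in number of medications and supplements in a single cohort with no comparator cannot be read as the impact of the study methods, which is what exploratory objective 2.3 asks for

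*Protocol*

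**What the plan says.** Section 2.3 of the protocol (Exploratory Objectives) sets this aim: "To assess the impact of introducing leading-edge scientific methods on the number of medications and/or dietary supplements taken by individuals". Section 2.4 (Exploratory Endpoints) gives two endpoints that match it. The first is "The number and change in the number of medications taken by an individual", read at four visits (months 6, 12, 18 and 24). The second does the same for supplements at the same visits.

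Section 3 describes the design: "This is a prospective, population-based observational study". It adds: "Participants and all participating health care providers are unblinded". Section 3.2.1 admits people aged 18 to 90, whether or not they have any medical history or symptoms. All participants enter the same programme of evaluation. Section 4.1 says that results go back to the participant and, if wanted, to a chosen provider, and that these two make any treatment decision.

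Section 7 states: "By design, the study will not employ formal hypothesis testing". Endpoints are to be summarised by means with standard deviations, medians with inter-quartile ranges, and other descriptive methods. The protocol names no control group, external reference, pre-enrollment trend or expected background change for these counts.

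**The concern.** The objective asks a causal question and the endpoint answers a descriptive one. Over 24 months people start and stop medications and supplements because they age, because a known disease progresses, or in the course of usual care. Others do so because a study scan or laboratory result was returned to them. The endpoint records only the total of all these changes.

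What is at stake is the sentence that the final report can write. If the plan is followed exactly, the report will have a mean or median change at each visit and an objective that calls it the impact of the methods. A rise could be entirely background. A flat line could hide a real reduction offset by background starts. The wording is not isolated: the Rationale (Section 1.2) also states the overall aim as assessing the impact of comprehensive evaluation.

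**Working it through.** The protocol states no effect size, standard deviation, start or stop rate, or sample size derivation for this endpoint, so there is no figure to reproduce. The check is an identity, with illustrative numbers that are all assumptions. I take change to mean change from enrollment.

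**Identity.** For the mean change in number per person up to a visit, let

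- Bs, Bt = starts and stops that would have happened without the study methods;
- Ms, Mt = additional starts and stops due to the methods.

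Then D = (Bs − Bt) + (Ms − Mt). The impact on the number is Ms − Mt. The plan observes D, and nothing in it supplies Bs − Bt.

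**1. No effect, nonzero reading.** Set Ms = Mt = 0, so D = Bs − Bt = r × t, where r is an assumed net background rate of 0.02 to 0.20 medications per person-year and t is time in years.

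| Visit | t | D at r = 0.02 | D at r = 0.20 |
|---|---|---|---|
| 6 months | 0.5 | 0.01 | 0.10 |
| 12 months | 1 | 0.02 | 0.20 |
| 18 months | 1.5 | 0.03 | 0.30 |
| 24 months | 2 | 0.04 | 0.40 |

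**2. Real effect, zero reading.** Over 24 months assume Bs = 0.3, Bt = 0.1, Ms = 0 and Mt = 0.2. Then D = (0.3 − 0.1) + (0 − 0.2) = 0, while the impact on the number is −0.2 per person. A Poisson simulation with these rates and 10,000 people gave a mean change of 0.006, a median of 0 and an inter-quartile range of 0 to 0. With the same background and no effect of the methods, the simulated mean was 0.203, again with a median of 0 and an inter-quartile range of 0 to 0. The two means differ by about the size of the effect. A reader who has only the first mean cannot know what the second would have been.

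**3. One reading, several truths.** A 24-month mean change of +0.2 fits each of these:

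- background +0.2, methods 0: 0.2 + 0 = 0.2;
- background 0, methods +0.2: 0 + 0.2 = 0.2;
- background +0.4, methods −0.2: 0.4 − 0.2 = 0.2.

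The impact is nil, an increase or a decrease, and the endpoint is the same. This does not depend on the rates chosen; only the size of the possible error does.

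**The case against.** **The objective is exploratory and the study openly descriptive.** This stands, and it limits the weight of the point. It does not remove the mismatch, because a description of change is not an assessment of impact.

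**The protocol nowhere says that a nonzero mean will be read as impact.** Also true. The fault is narrower: the objective promises an impact, and the endpoints tied to it cannot deliver one.

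**Each participant is their own control.** Section 1.2 offers this idea for laboratory measurements. It removes stable differences between people, but not the passage of time.

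**The plain number is listed as well as the change.** It has no comparator either.

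**The analysis plan or CRF may already cover this.** Neither is shown. A start/stop split, or a reason for each change, may be intended there. But an analysis plan cannot add a comparator that the protocol does not enroll, and the endpoints in 2.4 make no use of a reason.

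Two stronger readings are tempting, and the documents do not support them:

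- *The net count fails because it cancels starts against stops.* A participant who stops two drugs and starts two has no change in the number taken. The objective concerns the number, so zero is the right answer. Switching is a different target. The masking that matters is background starts offsetting stops due to the methods.
- *With up to 10,000 participants, drift would almost surely appear as a convincing effect.* That needs an assumed drift, an assumed standard deviation and a rule based on an interval excluding zero. The documents give neither figure, and Section 7 plans no test and names no interval.

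**Conclusion.** The concern holds in a limited form. Objective 2.3 claims an impact on the number of medications and supplements. The endpoints in 2.4 give the sum of background change and any effect of the methods, in one cohort with nothing to separate the two. The change in number remains useful as description, but it cannot be read as impact.

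The conclusion rests on the identity and the design, not on any assumed rate. The size of the error equals the background change, which the documents do not give. The range of 0.04 to 0.40 medications per person at 24 months is an illustration for assumed rates of 0.02 to 0.20 per year. Severity is minor: the objective is exploratory, no test is planned, and the main endpoints are untouched.

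**What to change.** 1. In Section 2.3, reword this item to: *describe changes in the number of medications and supplements, and those prompted by returned study results*.
2. In Section 2.4, keep the number and the change in number at each visit, as description.
3. In Section 2.4, add the number of medications, and the number of supplements, started and stopped since the last visit that the participant or provider attributes to a returned study result. Record this as yes/no for each change at the medical history already scheduled for every visit.

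The cost is a wording amendment and one yes/no CRF item per change, with no extra visits. The item follows the route described in Section 4.1, from returned result to treatment decision.

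The downside should be stated in the protocol. The attribution is partly self-reported by unblinded participants, and it gives no counterfactual: a change prompted by a study result might have come later in usual care. The reworded objective therefore makes a more modest claim, but one that the collected data can support.

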### 3. Study Design

This is a prospective, population-based observational study. Participants may be recruited from clinical sites that are actively participating in the Puer Research comprehensive evaluation model. Participants and all participating health care providers are unblinded.

#### 3.1. Study Schema

**Figure 1. Overall Study Schema.** The Baseline Visit includes a Medical history and physical examination (PE) Genomic Analysis, Biochemical/”Omics” Analysis and Non-Invasive Imaging. Subsequent visits at 6 months, 12 months, 18 months, 24 months and 36 months include slightly modified and targeted Medical history and PE, Biochemical/”Omics” Analysis and Non-Invasive Imaging, based on prior findings. Functional Assessments and Wearables and Quantified Self Assessments are included at the 6 months, 12 months, 18 months, 24 months and 36 months visits as determined by the Medical history and PE at the baseline visit.

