#### **3.3.2. Methodology**

Each of the visits include a combination of Medical history and PE, biochemical and “omics” assessments, non-invasive imaging assessments and optional functional assessments and wearables and quantified self-assessments.

*Medical history and PE* The Medical history and PE consists of a comprehensive “History and Physical Examination”, administered by a trained Research Associate. The elements of the history and physical examination are recorded in the Case Report Form (CRF).

- *Pregnancy Testing*

Pregnancy testing consists of a UPT for all WOCBP. The results must be negative for the subject to be able to participate in each visit.

- *Genomic Analysis*

- Whole genome sequencing (WGS) analysis (“DNA”)

- *Biochemical and “Omics” Assessments*

Biochemical and “omics” assessments consist of the following elements, using peripheral blood samples, and potentially urine, stool or saliva samples.

- Whole genome methylation analysis (“DNA methylation”)
- Whole transcriptome sequencing from circulating mononuclear cells (mRNA and miR)
- Proteomics profiling
- Metabolomics profiling
- Conventional biomarker analysis
- Urine analysis and profiling

- *Non-Invasive Imaging Assessments*

Non-invasive imaging assessment consists of the following elements, as directed, and determined by the Medical history and PE and biochemical and “omics” assessment, as described above. Imaging will follow the schedule in the table below, with an “x” indicating all participants and an “[x]” indicating imaging needed for risk-specific participants. Any deviation from the average population may trigger a dedicated organ specific MRI. Imaging may also be done at 18-, 24- and/or 36-month visits, depending on Medical history and PE at each visit, following the schedule at 6 or 12 months.

Imaging Procedure	Baseline	6 mos	12 mos
CT of head	x		
CT Angiogram of head/neck/face/sinus/orbits	x		
MRI of brain with and without contrast	x		x
MR Angiogram of head/neck time of flight			x
MRI of brain without contrast		[x]	
CT of chest, abdomen, and pelvis - mixed A/V	x	[x]	[x]
CT of chest, abdomen, and pelvis - venous only		[x]	x
MRI of spine without contrast (cervical/thoracic/lumbar)	x		x

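### Section 3.1 tailors follow-up assessments to prior findings, against the visit schedule and 3.3.2, so counts of new deviations depend partly on who was tested and for what

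*Protocol*

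**What the plan says.** Protocol 3.1, in the caption to the study schema, describes the follow-up visits: "Subsequent visits at 6 months, 12 months, 18 months, 24 months and 36 months include slightly modified and targeted Medical history and PE". The same sentence goes on to list omics "Analysis and Non-Invasive Imaging, based on prior findings".

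Protocol 3.3.2 describes the same components without tailoring by visit. On the clinical examination: "The Medical history and PE consists of a comprehensive" history and physical. On the laboratory side, biochemical and omics "assessments consist of the following elements, using peripheral blood samples, and potentially urine, stool or saliva samples", followed by a list that applies to no visit in particular. The schedule in the synopsis marks history/exam and biochemical/omics analysis at all six visits. It uses an as-needed label only for functional tests and wearables. Imaging is also marked at all six visits, but with a footnote that refers to 3.3.2 for detail.

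The imaging table in 3.3.2 distinguishes procedures for all participants from procedures for risk-specific participants. The text above the table makes imaging in general depend on the history/exam and omics results, and makes imaging at 18, 24 and 36 months optional, depending on the history/exam at that visit.

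The first main endpoint in 2.2 is the number of new deviations from the "baseline profile 12 months after enrollment that were previously not known at time of enrollment". The same count is taken at 6, 18 and 24 months. The last main endpoint is: "The number of new deviations identified by each employed modality".

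**The concern.** A count of previously unknown deviations can be read as a property of the participants only if the search is the same for everyone, or if its extent is known. Section 3.1 lets the search at follow-up depend on what was found before. The rest of the protocol, for history/exam and omics, does not. A site cannot follow both descriptions, and the schema defines neither the degree of modification nor what targeting means, so up to 20 sites may settle it differently.

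Three comparisons that the main endpoints invite are at stake: between visits, between modalities (which the second main objective needs in order to name the modality with the highest impact), and between sites. Section 7 plans descriptive statistics only, so uneven ascertainment passes directly into the reported counts. Unlike an analysis choice, content that was not collected at a visit cannot be recovered afterwards.

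**Working it through.** The protocol states no figure to reproduce here. The check sets the sections side by side, counts the imaging table, and links both to the endpoints.

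**Step 1. History/exam and omics.**

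| Source | History/exam at follow-up | Omics at follow-up |
|---|---|---|
| 3.1, schema caption | slightly modified and targeted | in the same list, which ends with the reference to prior findings |
| Synopsis schedule | marked at every visit, no condition | marked at every visit, no condition |
| 3.3.2 | comprehensive, no narrowing by visit | full list, no narrowing by visit |

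One source tailors; two do not.

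**Step 2. Imaging.** The 3.3.2 table has 10 procedures. Counting its entries:

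| Visit | For all participants | Risk-specific |
|---|---|---|
| Baseline | 7 | 0 |
| 6 months | 0 | 5 |
| 12 months | 6 | 1 |
| 18, 24, 36 months | none fixed | none fixed |

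- The six for all at 12 months are brain MRI with and without contrast, MR angiogram of head/neck, venous CT of chest/abdomen/pelvis, spine MRI, extremity x-rays and ultrasound.
- Of the 7 baseline procedures, 4 are repeated for everyone at 12 months, 1 only for risk-specific participants, and 2 (CT of head, CT angiogram of head/neck) at neither 6 nor 12 months: 4 + 1 + 2 = 7.
- The table's all-participants entries also sit uneasily with the sentence above the table that makes imaging in general depend on history/exam and omics.

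**Step 3. Link to the endpoints.** The main endpoints use four timepoints: 6, 12, 18 and 24 months. Imaging common to all participants exists at one of the four (12 months). At 18 and 24 months the decision to image rests on the history/exam, which 3.1 itself describes as targeted. Any narrowing there would carry through to imaging.

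**Step 4. What the count then measures.** For one procedure at one visit, let T = 1 if a participant is tested and 0 if not, and let D be the number of new deviations the test would show. The observed count is C = Σ T·D.

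- If T = 1 for everyone, C = Σ D, and C divided by the number of participants is the mean of D.
- If T depends on earlier results, C ≤ Σ D for that procedure. C divided by the number tested is the mean of D in a selected group, which may be higher or lower than the overall mean.
- Targeting may also add tests: 3.3.2 allows a deviation to prompt a dedicated organ MRI. The net direction for the total count is therefore not determined.

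To put a number on this one needs the share with T = 1 and the rates of D in the tested and the untested. The protocol gives none of these.

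**The case against.** The strongest case on the other side is that the broad search is still there:

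- The 3.1 sentence is a figure caption. It says the assessments are modified only slightly, and it nowhere says that unflagged areas are dropped.
- It can be parsed so that the targeting applies only to history/exam and the prior findings only to imaging.
- The omics elements in 3.3.2 are whole-platform assays that would not naturally be run in part.
- At 12 months, the first-listed endpoint, six imaging procedures cover head and neck, spine, trunk, extremities and reproductive organs/bladder for everyone.
- Section 5.3 adds an open query for new symptoms at each contact.
- How counts are tabulated may be left to a statistical analysis plan that is not shown.

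Much of this stands. A reader might infer from 3.1 that new problems outside areas already flagged are not looked for and are missed. The protocol does not support that, given the 12-month table, the schedule and the symptom query. A reader might also wish to quote a percentage of deviations lost. Any such figure would only return the share assumed to be re-examined, for which the protocol offers no value. Nor is it established that participants with a clean baseline are searched least, since that depends on sites letting the caption override the schedule.

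What the objection does not remove is the conflict itself. The symptom query sits under adverse event reporting and will not pick up silent molecular or imaging changes. The 12-month table does nothing for examination or omics content, or for imaging at the other three timepoints. What is collected at each visit is for the protocol to settle, and an analysis plan cannot supply it later.

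**Conclusion.** The point holds as an internal inconsistency with consequences for the main endpoints.

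- **History/exam and omics.** The tailoring rests on the single sentence in 3.1. It contradicts the synopsis schedule and 3.3.2, and whether it changes what is collected depends on how sites read it.
- **Imaging.** Selective testing is explicit and needs no inference. No procedure is common to all participants at three of the four main-endpoint timepoints (6, 18 and 24 months), against six at 12 months.

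As written, counts of new deviations are not directly comparable between 12 months and the other visits, between modalities applied to different subsets, or between sites that read the schema differently. The size and net direction of the effect cannot be computed from the protocol. The conclusion rests on the current text and on the reading that the reference in 3.1 to prior findings covers all three components. On the narrower reading, the imaging part is unaffected.

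**What to change.** 1. Reconcile 3.1 with the synopsis schedule and 3.3.2. State, for each endpoint visit, which history/exam, omics and imaging items every participant has and which are added because of risk or earlier findings. In 3.3.2, also reconcile the general sentence on directed imaging with the table entries for all participants.
2. In 2.2, count new deviations on the items common to all participants at that visit. Report deviations found only through risk-specific or finding-driven tests on a separate line, by modality, with the number of participants tested.
3. Do not extend imaging to more participants for this purpose. Where a visit has no common imaging, say so, and do not compare its imaging count directly with the 12-month count.

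The cost is a change of protocol wording, some extra tabulation and smaller headline counts, because finding-driven detections move to their own line. Assessment costs rise only where sites had planned to trim items that the schedule already marks.
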